**Table 8.2-1: Inclusion Criteria**

Inclusion Criteria	

1. Subjects indicated for the treatment of AF with the Cryoablation System according to current and future Guidelines and system indications for use;

2. Subjects who are willing and capable of providing informed consent;

3. Subjects who are willing and capable of participating in all testing associated with this clinical study at an approved clinical investigational center;

4. Subjects whose age is 18 years or above, or who are of legal age to give informed consent specific to state and national law.

--------------------	---

### 8.3. *Exclusion Criteria*

Subjects who meet any one of the following criteria (Table 8.3-1) cannot be included in this study or will be excluded from this clinical study.

**Table 8.3-1: Exclusion Criteria**

Exclusion Criteria	
 
1. Any known contraindication to an AF ablation or anticoagulation, including those listed in the instructions for use;
 
2. Subjects with indication for treatment of AF that is not according to current and future Guidelines and system indications for use;
 
3. Atrial fibrillation secondary to electrolyte imbalance, thyroid disease, or any other reversible or non-cardiac cause;
 
4. Known or pre-existing severe Pulmonary Vein Stenosis;
 
5. Evidence of myxoma, LA thrombus or intracardiac mural thrombus;
 
6. Previous cardiac surgery (e.g. ventriculotomy or atriotomy, CABG, PTCA, stent procedure) within 90 days prior to enrollment;
 
7. Implantable cardiac device procedure (e.g. PM, ICD, CRT) within 30 days prior to enrollment;
 
8. Implanted Left Atrial Appendage Closure device prior to the index procedure
 
9. Interatrial baffle, closure device, patch, or patent foramen ovale (PFO) occluder;
 
10. Subjects with severe valvular disease OR with a prosthetic – mechanical or biological - heart valve (not including valve repair and annular rings);
 
11. Presence of any pulmonary vein stents;
 
12. Active systemic infection;
 
13. Vena cava embolic protection filter devices and/ or known femoral thrombus;
 
14. Any previous history of cryoglobulinemia;
 
15. History of blood clotting or bleeding disease;
 
16. Any prior history of documented cerebral infarct, TIA or systemic embolism (excluding a post-operative deep vein thrombosis (DVT)) <math>\leq</math> 180 days prior to enrollment;
 
17. Subjects who are hemodynamically unstable;
 
18. The subject is unable or not willing to complete follow-up visits and examination for the duration of the study;
 
19. Life expectancy <math>\leq</math> 1 year per investigator's opinion;
 
20. Women of childbearing potential who are, or plan to become, pregnant during the time of the study (method of assessment upon investigator's discretion);
 
21. Unrecovered/unresolved Adverse Events from any previous invasive Procedure;
 
22. Subjects who are currently enrolled in another investigational study or registry that would directly interfere with the current study, except when the subject is participating in a mandatory governmental registry, or a purely observational registry with no associated treatments; each instance must be brought to the attention of the sponsor to determine eligibility.
 

--------------------	---

## 9. Subject Accountability

### 9.1. *Point of Enrollment*

Investigators will select subjects who are appropriate for study inclusion as per eligibility criteria as specified under section 8.2 and 8.3. Subjects who have given written informed consent are considered enrolled in the study. All enrolled subjects will be counted against the enrollment ceiling of maximum 400 subjects. A total of 199 De Novo TREATMENT subjects with paroxysmal atrial fibrillation will serve for PMCF reporting purposes. No study-related activities, testing, procedures, etc. can take place until the Informed Consent Form (ICF) is signed and dated by the subject. Screening tests that are part of standard of care can be used to determine pre-eligibility. Data from exams performed prior to consent/enrollment (e.g. TTE) will be collected as medical history data after the subject is consented/enrolled in the study. It is the investigator's site responsibility to assess eligibility criteria before obtaining the Informed Consent Form.

### 9.2. *Withdrawal*

All subjects enrolled in the clinical study (including those withdrawn from the clinical study) shall be accounted for and documented. If a subject withdraws from the clinical study, the reason(s) shall be reported. Withdrawn subjects will not be replaced.

Reasons for withdrawal include but are not limited to physician discretion, subject choice to withdraw consent, lost to follow-up, or death. While study withdrawal is discouraged, subjects may withdraw from the study at any time, with or without reason, and without prejudice to further treatment. All applicable case report forms up to the point of subject withdrawal and a "End of Study" form must be completed.

Every effort should be made to obtain full information on any ongoing reportable adverse events up to the point of withdrawal. All open reportable adverse events should be closed or documented as chronic. Data collected up to the point of subject withdrawal may be used, unless any local regulations apply. Additional data may no longer be collected after the point at which a subject has been withdrawn from the study or withdraws his/her consent, for whatever reason. If such withdrawal is due to problems related to device safety or performance, the investigator shall ask for the subject's permission to follow his/her status/condition.

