### 11.1.1.2. Sample Size

### 11.1.1.3. Statistical Methods

The 12 month (365-day) primary safety event-free rate will be calculated using Kaplan-Meier methodology. Subjects who withdraw from the study prior to 12 months without experiencing an event will be censored on the date of withdrawal. The 95% one-sided lower confidence limit of the observed safety event-free rate will be compared to the performance goal of 86%. If the lower confidence limit is greater than the performance goal, the null hypothesis will be rejected. The lower confidence limit will be calculated as the pointwise confidence limit using the log-log methodology.

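### Section 9.2 does not separate leaving study visits from withdrawing consent to data collection, so treated subjects withdrawn at physician discretion are lost to both primary analyses and may be censored informatively

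*Combined protocol and SAP*

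**What the plan says.** Section 9.2 lists why a subject may leave: "Reasons for withdrawal include but are not limited to physician discretion, subject choice to withdraw consent, lost to follow-up, or death". Its rule on later data has two triggers, joined by 'or': "Additional data may no longer be collected after the point at which a subject has been withdrawn from the study or withdraws his/her consent". The sentence ends by making the reason immaterial.

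The next sentence makes one exception. It opens "If such withdrawal is due to problems related to device safety or performance" and continues that "the investigator shall ask for the subject's permission to follow his/her status/condition".

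Information from before withdrawal is kept: "Data collected up to the point of subject withdrawal may be used, unless any local regulations apply". For adverse events, "Every effort should be made to obtain full information on any ongoing reportable adverse events up to the point of withdrawal", and open reportable events are to be closed or recorded as chronic. "Withdrawn subjects will not be replaced".

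Section 11.1.1.3 (safety) gives the Kaplan-Meier rule: "Subjects who withdraw from the study prior to 12 months without experiencing an event will be censored on the date of withdrawal". Section 11.1.2.3 (effectiveness) repeats that sentence. Section 10.13, by contrast, has every TREATMENT subject followed for 12 months after the index procedure. The visible text contains no sensitivity analysis for withdrawals.

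**The concern.** The study treatment is a single index procedure. Once it has been done, withdrawing a subject stops no study treatment and only ends observation. Under section 9.2, a physician's decision to take a subject out therefore has the same effect on the data as the subject's own refusal, although the subject may have refused nothing.

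Kaplan-Meier censoring is unbiased only if those who leave have the same later risk as those who stay. A physician may take a subject out because that subject is doing badly or is being treated elsewhere, and the assumption is then doubtful. Both primary endpoints are compared with fixed performance goals in a single-arm study, so no control arm shares an upward bias.

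**Working it through.** **Step 1. Which subjects are affected (sections 9.2 and 9.4)**

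| Route out, after cryoablation | Consent to data withdrawn? | Later data under 9.2 |
|---|---|---|
| Subject withdraws consent | Yes | Stops, as it should |
| Lost to follow-up, or death | Not applicable | None obtainable |
| Device safety or performance problem | Not necessarily | Permission to follow is sought; use in the analysis not stated |
| Physician discretion, other reasons | Not necessarily | Stops |

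The last row is the main gap. The third row needs clarifying.

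**Step 2. Which endpoint components can be missed**

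- *Effectiveness (section 6.2.2).* Documented recurrence, repeat procedure, cardioversion, and a new or increased AAD all count from day 91 to day 365. The Month 3 Holter is optional and the first required one is at Month 6, days 150-210 (sections 10.8 and 10.9). A subject withdrawn at Month 4 with no documented recurrence is censored. A repeat procedure or cardioversion elsewhere the following month is not collected.
- *Safety (section 6.2.1).* Eleven of the 15 components are acute, ending at day 7 or discharge, whichever is later, so a Month 4 withdrawal cannot hide them. Four are chronic. Phrenic nerve injury is the clearest case, because it counts only if unrecovered at 12 months. A subject withdrawn at Month 6 with unresolved palsy has the event recorded as chronic, but the Month 12 status that defines the endpoint is never obtained. The plan does not say how that subject is classified.

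**Step 3. Size for effectiveness**

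Inputs from the plan: N = 199 (section 7.1), goal 50% (section 11.1.2.1), one-sided 95% log-log lower limit (section 11.1.2.3). The sample size sections are not visible, so 199 cannot be reproduced and no withdrawal rate is available.

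Assumptions: k = 4 to 12 subjects leave this way (4/199 = 2%, 12/199 = 6%). Their later failure risk p is 70-90%, against 35% in those who stay. The 35% is consistent with the 65-70% efficacy that section 4.1 cites for an existing cryoballoon.

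Censoring in effect gives the k subjects the later risk of those who stay, so

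overstatement ≈ k × (p − 0.35) / 199

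- Low end: 4 × (0.70 − 0.35)/199 = 1.4/199 = 0.7 points
- High end: 12 × (0.90 − 0.35)/199 = 6.6/199 = 3.3 points

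**Step 4. Would that change the conclusion?**

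With no censoring, the lower limit is

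L = exp{−exp[log(−log S) + 1.645 × √((1 − S)/(199 S)) / |log S|]}

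- S = 112/199 = 56.3%: L = 50.3%. This is the smallest passing count.
- At the high end, 65% among those who stay means a true rate of 65 − 3.3 = 61.7%. The nearest count is 123/199 = 61.8%: L = 55.9%, still above 50%.

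**Step 5. Worst-case bound**

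In 3,000 simulated trials per setting, the true effectiveness rate was set at the 50% goal, with failures uniform over days 91-365. A share f of would-be failures was withdrawn just before the event.

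| f | Share of cohort withdrawn | Mean Kaplan-Meier rate | One-sided type I error |
|---|---|---|---|
| 0 | 0 | 49.9% | 3.8% |
| 10% | 5% (about 10 subjects) | 53.6% | 25% |
| 20% | 10% (about 20 subjects) | 57.4% | 62% |

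Every withdrawal here is a certain failure removed at the worst moment, so this is a bound and not an expectation. The same simulation for safety (goal 86%) gives 3.6% at f = 0 and about 11% at f = 10% (about 3 subjects). That figure overstates the exposure, because it spreads all events over days 91-365 although most safety components are acute.

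**The case against.** Several points on the other side stand.

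- *Device-related withdrawals.* A reader of the general sentence alone might infer that all collection ends even when the device is the reason. The documents do not support that. The following sentence is a specific exception and requires permission for follow-up to be sought. What stays open is whether the data obtained reach the eCRF and the analysis.
- *Counted as successes.* A reader might also infer that withdrawn subjects are scored as event-free at 12 months. They are not. They leave the risk set, only those without a prior event are censored, and an endpoint event that prompted the withdrawal already counts as a failure.
- *The design tracks later treatment.* Repeat ablation has its own eCRF (section 10.12), symptom-driven visits are collected (section 10.11), and interventions and drug changes are recorded at each clinic visit. Withdrawal is discouraged and reasons must be reported. A recurrence documented, or a counted intervention made, after the blanking period and before a Month 4 withdrawal is already a failure. Only what has not yet been documented or treated escapes.
- *Safety knife-edge.* With no censoring, 19 events in 199 give a lower limit of 86.4% (pass) and 20 give 85.8% (fail). It is tempting to conclude that one unseen event decides the trial. Any threshold test has such a margin, and it matters only if the observed count falls exactly there. It is not an estimate of bias.
- *Limits of the remedy.* Rhythm recurrence counts through clinical visits, ECG and 24-hour Holter. Telephone or record follow-up cannot replace a Holter.

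These points narrow the concern but do not remove it. Nothing in section 9.2 keeps a consenting subject under observation after a non-device physician withdrawal, and that sits badly with the 12-month follow-up in section 10.13.

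**Conclusion.** The point holds in this limited form. Outside device-related withdrawal, section 9.2 ties the end of data collection to leaving the study rather than to withdrawal of consent for data, and both primary analyses censor at that date. The censoring may be informative, and the likely direction is upward: mainly for effectiveness, less for safety, where only the four chronic components are exposed.

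The size is unknown because no withdrawal rate is given. The 0.7 to 3.3 points for effectiveness rest entirely on the assumed 2-6% leaving, 70-90% later failure and 35% reference risk. At 65% failure-free among those who stay, a bias of that size would not overturn a pass against 50%; it would matter more if the true rate were near the goal. No safety bias can be estimated from the documents. This is an inexpensive improvement to the plan and does not show that the primary conclusions would be wrong.

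**What to change.** In section 9.2:

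1. Limit the stop on data collection to subjects who withdraw consent for further data. Keep all other TREATMENT subjects in follow-up to Month 12, with scheduled visits, ECG and Holter where possible. Where visits are not possible, use telephone contact or routine records to capture interventions, AAD changes and adverse events.
2. State that data obtained with permission after a device-related withdrawal are entered on the eCRF and count for both primary endpoints to day 365. Align sections 11.1.1.3 and 11.1.2.3 so that these subjects are censored at last available follow-up.

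Cost: protocol and consent-form wording, which needs EC approval (section 14.3), and a few contacts or record checks. No procedures are added beyond those already scheduled. The downsides are slightly less favourable rates and less complete rhythm monitoring in the few subjects followed remotely.

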### 9.3. *Lost to Follow-Up*

A subject will be considered lost to follow-up if he/she fails to return to scheduled visits as per Data Collection Schedule (Table 10.1-1), and is unable to be contacted by the study site staff.

The following actions must be taken if a subject fails to return to the clinic for a required study visit:

- The site will attempt to contact the subject to reschedule the missed visit and counsel the subject on the importance of maintaining the assigned visit schedule and ascertain if the subject wishes to and/or should continue in the study.

- Before a subject is deemed lost to follow-up, the investigator or designee will make every effort to regain contact with the subject (3 attempts, including telephone calls and/or a certified letter to the participant's last known mailing address or local equivalent methods, where possible). These contact attempts must be documented in the subject's medical record or study file and in the "End of Study" eCRFs.
- Should the subject continue to be unreachable, he or she will be considered lost to follow-up from the study.

#### **9.4. *Subject Status and Classification***

##### **Consent Ineligible (Screening Failures)**

A subject who has given written informed consent but is found not to meet eligibility criteria before undergoing the index procedure and before having the study device inserted in the body, will be classified as "Consent Ineligible".

Subjects determined to be Consent Ineligible count towards the enrollment ceiling but will not be used for analysis of the endpoints. The original signed and dated Informed Consent must be maintained in the center's subject file. A subject identification number (ID) will be assigned in the EDC system.

For consent ineligible subjects, at the minimum the following forms must be completed:

- Enrollment eCRFs;
- Adverse Event eCRFs for any reportable event (as defined in section 17) that occurs after signing the Informed Consent, up to the point of subject withdrawal;
- Protocol Deviation eCRF, if applicable;
- End of Study eCRF.

##### **Intent**

A subject who has given written informed consent, meets eligibility criteria, but does not have any study devices inserted into the body will be classified as "INTENT". This includes subjects that had been prepared for the procedure (e.g. medication administered) and/or who had non-study devices inserted into the body. Subjects that are enrolled in the study but do not undergo ablation procedure within 90 days from consent signature date must not be reconsented and will be withdrawn from the study and classified as "INTENT". These subjects won't be allowed to be re-enrolled in the study.

There are no follow-up requirements for Intent subjects. Intent subjects will count towards the enrollment ceiling but will not be used for analysis of the endpoints. The original signed Informed Consent must be maintained in the center's subject file. A subject ID will be assigned in the EDC system.

For intent subjects, at the minimum the following forms must be completed:

- Enrollment and Baseline eCRFs;
- Adverse Event eCRFs for any reportable event (as defined in section 17) that occurs after signing the Informed Consent, up to the point of subject withdrawal;
- Protocol Deviation eCRF, if applicable;
- End of Study eCRF.

## Attempt

A subject who has given written informed consent, and has any study device inserted into the body but does not receive any Cryoablation application will be classified as "ATTEMPT." Attempts subjects will count towards the enrollment ceiling and will be used for analysis of the endpoints as per section 11.3.1. The original signed Informed Consent must be maintained in the center's subject file. A subject ID will be assigned in the EDC system. These subjects won't be allowed to be re-enrolled in the study.

Attempt subjects will be followed up to 7 days after index procedure or until discharge, whichever is later, for safety purposes. All applicable case report forms in the EDC system will be completed. The original signed Informed Consent and any relevant documentation must be maintained in the center's subject file.

For attempt subjects, at the minimum the following forms must be completed:

- Enrollment and Baseline eCRFs;
- Index Procedure eCRFs;
- Pre-Discharge eCRFs and Day 7 follow-up contact eCRF (if applicable);
- Adverse Event eCRFs or Device Deficiency eCRF for any reportable event (as defined in section 17) that occurs after signing the Informed Consent, up to the point of subject withdrawal;
- Protocol Deviation eCRF, if applicable;
- End of study eCRF.

## Treatment

Any subject who has given written informed consent and has the specified study device inserted into the body and received at least one Cryoablation application will be classified as "TREATMENT". These subjects are followed in accordance with the Data Collection Schedule (Table 10.1-1) and included in all study analyses. A subject ID will be assigned in the EDC system. For TREATMENT subjects, all applicable case report forms per the protocol will be completed. Treatment subjects do count towards the enrollment ceiling and will be used for analyses of the endpoints. The original signed Informed Consent and any relevant documentation must be maintained in the center's subject file.

### 9.5. *End-of-Study Definition*

The clinical study is considered completed when subjects are no longer being examined or the last subject's last study visit has occurred. The subject's end of study is defined as completion of the last visit or procedure as shown in the Data Collection Schedule (Table 10.1-1) in the study.

## 10. Study Methods

### 10.1. *Data Collection*

Each Treatment subject will be followed at index procedure, at pre-discharge visit, at the month 3 follow-up, month 6 follow-up and month 12 follow-up. To reliably capture subject status at study end, the month 12 follow-up must be scheduled within  $365 \pm 30$  days following the index procedure. The data collection schedule is shown in Data Collection Schedule (Table 10.1-1).

Table 10.1-1: Data Collection Schedule

Procedure / Assessment	Enrollment Baseline	Index Procedure (Day 0)	Blanking period			Effectiveness Evaluation period			Repeat (additional) ablation procedure
			Pre-Discharge (0-7 days post procedure)	Day 7 contact  (day 7 + 7 days)	Month 3 Follow-Up (91±14 days)	Month 6 Follow-Up (180±30 days)	Month 12 Follow-Up (365±30 days)	Additional Follow-up	
Informed consent process, including informed consent signature date	X								
Eligibility criteria	X								
Demographics	X								
Medical history	X								
LVEF, LA diameter and LA volume	X 								
Physical assessment	X		X		X	X	X	(X)	
LA assessment imaging and thrombus assessment		(X) 							(X) 
Procedural Data		X							X
3D Mapping information		(X)							(X)
12-Lead ECG	X	X	X		X	X	X	(X)	X
Holter Monitor (24 hours)					(X)	X	X	(X)	
Documentation of intervention for AF/AT/AFL (if any)			X		X	X	X	(X)	
Medications	X	X	X		X	X	X	(X)	X
Protocol Deviations	X	X	X	X	X	X	X	(X)	X
Adverse Event Assessment	X 								

X: Required; (X): Optional, per site standard of care;

 Per investigator's method. It is recommended to have the assessment within 180 days prior to enrollment;

 Assessment of left atrium anatomy, pulmonary veins anatomy and rule-out presence of thrombus is strongly recommended and to be performed according to site's standard of care practice - Assessments can be performed using CT, MRI, pulmonary venogram, ICE, TEE or other;

 It is recommended to have the LA assessment performed within 180 days prior to enrollment;

 If subject is discharged prior to day 7 post-index procedure, a (telephone) contact at day 7 (+ 7 days) is required to assess any post-discharge adverse events and complications;

 Adverse event assessment will be performed as from enrollment until study completion;

 A 24H Holter monitor is required at 6 and 12 months follow-up for all subjects.

